7.2.5 Treatment of Hypomagnesemia

In the event that a patient experiences Grade 3 or 4 hypomagnesemia, treatment with iv magnesium sulphate 6-10 g or equivalent should be given at least twice a week until magnesium levels are \leq Grade 1.

A 12-lead ECG should be performed prior to administration of the next dose of Sym004 for monitoring of QT prolongation which may result in Torsade de Pointes (TdP) arrhythmias. In the event of TdP arrhythmia or any other life-threatening cardiac arrhythmia, the patient should be withdrawn from treatment with Sym004.

7.3 Blinding

Not applicable as this is an open-label trial.

7.4 Drug Accountability and Compliance Check

The Investigator is responsible for ensuring accountability for the IMP, including maintenance of IMP accountability records.

IMP accountability records will include a full inventory of the IMP including:

- Confirmation of IMP delivery to the trial site
- Record of each dose dispensed
- The return of unused IMP to the Sponsor or designee

Records will specify dates, quantities, batch numbers, use-by dates and patient numbers, as applicable.

The Investigator, or designee, should maintain records that adequately document:

- That the patients were provided the doses specified by the CTP, and
- That all IMP provided by the Sponsor was fully reconciled

7.5 Concomitant Medication/Therapy

7.5.1 Allowed Concomitant Medication/Therapy and Procedures during the Trial

Patients may receive their current concomitant medication and any medication considered necessary for the welfare of the patient during trial, except if listed in [Section 7.5.2](#).

Furthermore, the following medications and procedures are permitted during the trial:

- Premedication with standard therapies prior to Sym004 administration to reduce the risk of IRRs
- Prophylaxis and treatment of Sym004 and FOLFIRI related toxicities
- Prophylactic use of blood products and growth factors after Cycle 1. Interventional/therapeutic use is allowed at any time
- Radiotherapy for pain control against non-target lesions, as long as it does not influence bone marrow function

7.5.2 Prohibited Concomitant Medication/Therapy and Procedures during the Trial

The following medications and procedures are not allowed from C1/D1, or as specified in the inclusion/exclusion criteria, until the EOT Visit:

- Anti-cancer treatment, including cytotoxic or cytostatic agents, hormonal therapy (except as physiologic hormone replacement), other anti-EGFR antibodies or anti-EGFR small molecule inhibitors
- Radiotherapy against target lesion(s)
- Systemic immunosuppressive or systemic hormonal therapy with the exception of the following allowed therapies:

- a. Hormonal therapy (e.g., Megace) for appetite stimulation
 - b. Nasal, ophthalmic, inhaled, and topical glucocorticoid preparations
 - c. Oral replacement glucocorticoid therapy for adrenal insufficiency
 - d. Low-dose maintenance steroid/hormonal therapy for other conditions (excluding steroid tapers for brain edema/metastases/radiation)
 - e. Hormonal contraceptive therapy
- Prophylactic use of hematopoietic growth factors during Cycle 1
 - Major surgery that would preclude the patient from complying with the requirements of the protocol

If any one of the above listed medications/procedures becomes necessary during the trial, the patient must be withdrawn from Sym004 and FOLFIRI and the EOT Visit should be performed. The 1M FUP Visit should then be conducted, no less than 1 month (28 +7 days) after withdrawal from trial treatments.

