6.3.1 Withdrawal from Treatment with Sym004 and/or FOLFIRI

The patient must be withdrawn from treatment with Sym004 and/or FOLFIRI in the event of any of the following:

- A DLT considered by the Investigator to require treatment discontinuation (See [Section 9.5](#)) (dose-escalation cohorts only)
- Occurrence of an AE considered by the Investigator to require treatment discontinuation
- CTCAE Grade 4 skin toxicity (applies to Sym004 only)
- FOLFIRI-related toxicity not controlled by dose-reduction guidelines are outlined in [Table 7](#) in [Section 7.2.1.1](#) and [Appendix 2](#)
- PD, verified by CT/MRI according to RECIST v1.1 ([Appendix 1](#))
- Treatment failure not meeting the criteria for PD, but considered by the Investigator to require treatment discontinuation
- Requirement for a significant surgical procedure

NOTE: Patients requiring a minor surgical procedure (e.g., port placement, skin abscess drainage) may continue at the Investigator's discretion following discussion with the Sponsor or designee. A brief interruption in therapy may be considered
- An intercurrent illness which, in the opinion of the Investigator, would prevent completion of trial-related evaluations
- The Investigator judges it necessary due to medical reasons
- Use of prohibited concomitant medication, as defined in [Section 7.5.2](#)
- Pregnancy

- Significant deviation from the protocol or eligibility criteria. Such patients will be considered protocol violations and may be discontinued from treatment after discussion with the Sponsor
- Noncompliance with trial procedures may require discontinuation after discussion with the Sponsor
- Patient withdrawal of consent and election to discontinue treatment. (Patients may leave the trial at any time for any reason if they wish to do so, without any consequences)
- Termination of the trial by the Sponsor

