Appendix 2 FOLFIRI Guidelines for Dose Modifications and Delays

The following sections include guidelines for dose modifications and delays associated with specific symptoms.

Neutropenia or Thrombocytopenia

The following guidelines are based on the worst grade of neutropenia or thrombocytopenia observed during a 2-week dosing period (*Please note: For the purposes of this trial, two consecutive 2-week dosing periods equals 1 cycle*):

- Grade 2 neutropenia or thrombocytopenia: 5-FU and irinotecan may be resumed at the previous dose levels for the next administration, provided ANC $\geq 1.5 \times 10^3/\mu\text{L}$ ($1.5 \times 10^9/\text{L}$) and platelets $\geq 100 \times 10^3/\mu\text{L}$ ($100 \times 10^9/\text{L}$). If hematologic criteria are not met, doses of 5 FU and irinotecan should be reduced for the next administration.
- Grade 3 or 4 neutropenia or thrombocytopenia: Interrupt or skip 5-FU and irinotecan. Skipped doses are not to be made up. For subsequent administrations, 5-FU and irinotecan should continue at 1 dose level lower.
- Febrile neutropenia (ANC $< 1.0 \times 10^3/\mu\text{L}$ [$1.0 \times 10^9/\text{L}$] and fever $\geq 38.5^\circ\text{C}$): Interrupt or skip 5-FU and irinotecan. If fever resolves, neutropenia resolves to ANC $\geq 1.5 \times 10^3/\mu\text{L}$ ($1.5 \times 10^9/\text{L}$), and platelets are $\geq 100 \times 10^3/\mu\text{L}$ ($100 \times 10^9/\text{L}$), 5-FU and irinotecan should continue at 1 dose level lower for the next administration. Skipped doses are not to be made up.

If a dose delay is required due to any grade of neutropenia or thrombocytopenia, prophylactic use of granulocyte colony-stimulating factor (G-CSF)/granulocyte macrophage colony stimulating factor (GM-CSF) prior to the next administration of FOLFIRI is permitted at investigator discretion, provided that G-CSF/GM-CSF administration is completed ≥ 48 hours prior to administration of FOLFIRI.

Diarrhea

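### Prophylactic growth factor in Cycle 1 is permitted by Appendix 2 but prohibited, with withdrawal, by Sections 7.5 and 6.3.1, and a patient affected has no single DLT-evaluability status

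*Protocol*

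**What the plan says.** Three places in the body of the protocol point the same way. Section 7.5.1 allows "Prophylactic use of blood products and growth factors after Cycle 1. Interventional/therapeutic use is allowed at any time". Section 7.5.2 prohibits "Prophylactic use of hematopoietic growth factors during Cycle 1" and adds: "If any one of the above listed medications/procedures becomes necessary during the trial, the patient must be withdrawn from Sym004 and FOLFIRI". Section 6.3.1 includes among its mandatory reasons for stopping treatment "Use of prohibited concomitant medication, as defined in" Section 7.5.2. There the consequence is withdrawal from Sym004 and/or FOLFIRI, whereas 7.5.2 names both.

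Appendix 2, on neutropenia and thrombocytopenia, says otherwise. "If a dose delay is required due to any grade of neutropenia or thrombocytopenia", then "prophylactic use of granulocyte colony-stimulating factor (G-CSF)/granulocyte macrophage colony stimulating factor (GM-CSF) prior to the next administration of FOLFIRI is permitted at investigator discretion". The one condition is that the growth factor is finished at least 48 hours before FOLFIRI. The appendix neither excludes Cycle 1 nor refers to Section 7.5.

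**The concern.** Cycle 1 is the DLT observation period (Section 9.5.2), and the neutropenia DLTs in Section 9.5.1 depend on grade, fever and duration. Whether prophylactic growth factor may be given in that period should therefore have one answer at every site. As written, a site following Appendix 2 may give it and keep treating, while a site following Sections 7.5.2 and 6.3.1 must withdraw the patient for the same act. At stake are consistent treatment of dose-escalation patients, comparable neutrophil observations across the cohort, and a clear rule on whether the patient counts towards the MTD.

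**Working it through.** The protocol states no figure on this point, so there is nothing to reproduce. The check sets the passages side by side.

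1. **Does Appendix 2 bind in Cycle 1?** Section 7.2.1.1 sends sites to it for FOLFIRI modifications. It was adapted to this trial's cycles ("two consecutive 2-week dosing periods equals 1 cycle"), so it covers the Day 15 dose of Cycle 1. No text says which passage prevails, and Section 17 allows no waivers.

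2. **Can the rules meet inside the DLT period?** Under Section 7.2.1.1, FOLFIRI is delayed if ANC is below 1.5 × 10⁹/L or platelets are below 100 × 10⁹/L, and it resumes with a scheduled Sym004 dose. After Day 15 the next is Day 1 of Cycle 2: 15 + 14 = Day 29. Finishing 48 hours earlier means by 29 − 2 = Day 27. Growth factor under Appendix 2 would thus fall between about Day 15 and Day 27, within the 28-day period (visits carry ± 2 days).

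3. **How is that act treated?**

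| Passage | Prophylactic growth factor, Day 15 to 27 of Cycle 1 |
|---|---|
| Appendix 2 | Permitted if the investigator chooses |
| Section 7.5.1 | Allowed only after Cycle 1 |
| Section 7.5.2 | Prohibited; withdraw from both treatments if it becomes necessary |
| Section 6.3.1 | Use is a reason for withdrawal from one or both treatments |

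4. **What can it do to a DLT?** This depends on why Day 15 was delayed.
   - Grade 3 or higher, related to Sym004 or the combination: criterion 5 (Cycle 1 not completed at the assigned doses) can already make this a DLT. Later growth factor does not undo it. Criterion 6 (delay over 2 weeks) also needs Grade 3 or higher, so for a Day 15 delay it adds little.
   - Lower-grade neutropenia: taking the ANC below 1000 per mm³ given with criterion 3a as the Grade 3 limit, this is an ANC from 1.0 to below 1.5 × 10⁹/L. It is not a DLT at that point. It could become one before Day 28 under 3a (Grade 3 or 4 with fever and antibiotics) or 3b (ANC below 500 per mm³ for more than 5 days). Growth factor could prevent that.
   - Attributed to FOLFIRI alone: not a DLT under any criterion.

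5. **How is the patient counted?** Section 9.5.2 requires two full combination doses. A patient whose Day 15 FOLFIRI moves to Day 29 has had one in Cycle 1 and is a non-completer. Section 6.4.1 asks whether the reason was a DLT; Section 10.2 asks whether it was drug toxicity.

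| Recorded reason for not completing Cycle 1 | Section 6.4.1 | Section 10.2 |
|---|---|---|
| Neutropenia that is not a DLT | Replaceable, not counted for the MTD | Stays in the DLT set |
| Withdrawal for prohibited medication | Replaceable, not counted for the MTD | Excluded, if this is read as not drug toxicity |

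In a cohort of three with no DLT, the first row gives 0 of 2 plus a replacement under 6.4.1, but 0 of 3 under 10.2. This mismatch exists even without growth factor. The forced withdrawal adds a second possible recorded reason, so the status can also depend on which reason is entered.

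**The case against.** The strongest reply is that this is a missing cross-reference. Three body sections agree, Appendix 2 is a general FOLFIRI guide for all cycles, and its permission is discretionary, so a Day 15 delay alone triggers neither rule. The point about discretion stands: the conflict arises only when a site elects prophylactic use. But Section 6.3.1 is triggered by use, whatever is made of necessity in 7.5.2, so an investigator who relies on Appendix 2 still meets a withdrawal rule. Agreement among the body sections is not a stated order of precedence.

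A reader might infer that Appendix 2 lets DLTs be hidden generally, or that the trial's DLT counts are unreliable. The documents do not support that. Criterion 5 already covers the more severe related delays. Therapeutic growth factor is allowed in Cycle 1, so neutrophil counts there would not be free of growth factor even after a correction. The ISMC confirms DLTs and reviews all reported adverse events (Section 12.1), and adverse events are recorded until the one-month visit even after withdrawal.

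It is also tempting to size the problem by noting that one patient moves a cohort from 0 of 3 to 1 of 3, or from 1 of 6 to 2 of 6. That is true of any single reclassification in a 3 + 3 design and says nothing specific about growth factors. The protocol gives neither the frequency of such delays nor the share of DLTs that growth factor would avert.

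Finally, Amendment 3 stopped accrual and declared the objectives no longer applicable. That limits the forward effect, but it does not settle how a Cycle 1 patient already treated is classified.

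**Conclusion.** The point holds as an internal contradiction in the current text, with a bounded statistical consequence. The same elective act after a delayed Day 15 FOLFIRI dose in Cycle 1 is both permitted and a reason for withdrawal. The route to an altered DLT count is narrow: mainly a lower-grade delay that would otherwise have progressed to criterion 3a or 3b before Day 28. The evaluability gap is firmer, because Sections 6.4.1 and 10.2 use different tests and can give one patient two answers.

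No number of affected patients can be derived. Only dose-escalation patients are concerned (9 to 18 planned), and among them only those with a Day 15 delay who were then given prophylactic growth factor. The conclusion assumes that Appendix 2 applies in Cycle 1 as its wording implies, and that delayed FOLFIRI resumes at Day 1 of Cycle 2 as Section 7.2.1.1 indicates. It is worth correcting because the correction is cheap.

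**What to change.** - Reconcile Appendix 2 with Sections 7.5.1, 7.5.2 and 6.3.1 so that one rule on prophylactic growth factors applies in Cycle 1, with one stated consequence for which treatments are stopped. The sponsor decides which clinical rule that is.
- Align Sections 6.4.1 and 10.2 on a single test for non-completion. State the DLT-evaluability status of a dose-escalation patient who received prophylactic growth factor in Cycle 1 or was withdrawn for it.
- Apply that status to the Cycle 1 data already collected, using the concomitant medication and withdrawal records, and describe any affected patient in the clinical trial report.

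The cost is a cross-reference or short sentence in Appendix 2, about one sentence across 6.4.1 and 10.2, and a check of existing records. Sample size and data collection do not change.

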7.6 Medical Care of Patients after End of Trial Participation

After completing participation in this trial, patients will be offered standard of care treatment in accordance with generally accepted medical practice and depending on the patient's individual medical need.

8 TRIAL ASSESSMENTS

8.1 Baseline Characteristics / Eligibility Assessments

8.1.1 Signing of Informed Consent

Prior to any protocol-related procedure, unless such testing was performed previously as part of the routine clinical management of the patient.

- Screening

NOTE: In the event a tumor biopsy is required for eligibility, informed consent may be obtained outside the 14-day screening period prior to C1/D1

8.1.2 Demographics

To include date of birth, sex, race and ethnicity.

- Screening

8.1.3 Medical History

To include details of prior and ongoing medical illnesses and conditions and prior surgical procedures not related to the primary diagnosis.

- Screening
- C1/D1 (prior to dosing)

8.1.4 Tumor Characteristics and Extent of Disease

To include details of diagnosis and date of initial diagnosis, Tumor Node Metastasis (TNM) staging at time of initial diagnosis, tumor histology, current location of metastases, date of most recent disease progression and mutation status.

- Screening

8.1.5 Prior Cancer Treatments

To include details of prior surgical procedures for the primary diagnosis, as well as prior radiotherapy, chemotherapy and/or biological targeted therapy, investigational treatments and/or procedures. Include dates of treatments, numbers of cycles, and best response to such treatments.

- Screening
- C1/D1 (prior to dosing)

8.2 Safety Assessments

To be performed within 14 days of C1/D1 (first dose of Sym004/FOLFIRI), unless otherwise specified.

8.2.1 Medication Survey

To include details of all medications and/or treatments taken other than Sym004 or FOLFIRI. Include generic name or brand name, indication for use, dose and frequency, route of administration, start and stop dates or if ongoing at 1M FUP Visit

- Starting from the date of Screening
- Until the date of the 1M FUP

8.2.2 Adverse Event Survey

For details about (S)AEs and (S)AE reporting, refer to [Section 9](#).

- Starting from signing the informed consent until the date of the 1M FUP

NOTE: Patients who sign the informed consent and are subsequently deemed to be screening failures will be followed for the occurrence of SAEs/AEs until it is determined they will not be participating in the trial

8.2.3 Dose-Limiting Toxicities Evaluation (Dose-Escalation Only)

For details about AEs meeting DLT criteria, refer to [Section 9.5](#).

- Starting from the first dose of trial drug (C1/D1)
- Reported during Cycle 1 with final assessment 14 days (± 2) after the second dose of Cycle 1 or prior to dosing on the scheduled Day 1 of Cycle 2 (C2/D1)

8.2.4 Vital Signs and Body Weight

To include temperature, heart rate, blood pressure, and body weight.

- Screening
- Day 1 and 15 of each cycle (prior to dosing)
- EOT
- 1 M FUP
- As clinically indicated

8.2.5 Performance Status

To be assessed by ECOG PS score.

- Screening

- Day 1 of each cycle (prior to dosing)
- EOT
- 1 M FUP
- As clinically indicated

8.2.6 Physical Examination

To include evaluation of: General appearance, head, ears, eyes, nose, throat, neck/thyroid, chest, cardiovascular system, abdomen, musculoskeletal system, pulses, lymph nodes, neurologic status and mental status. At Screening, include height (without shoes, rounded to nearest centimeter).

- Screening
- Day 1 of each cycle (prior dosing)
- EOT
- 1M FUP
- As clinically indicated

8.2.7 Dermatological Assessment

To be performed by a physician or qualified designee; complete skin examination

- Screening
- Day 1 and 15 of each cycle (prior to dosing)
- EOT
- 1M FUP
- As clinically indicated

8.2.8 Electrocardiogram

To include standard 12-lead ECG. The Investigator, or qualified designee, should document the evaluation of the ECG, including specification of any abnormality as clinically significant or not clinically significant.

- Screening
- EOT
- In the event of \geq Grade 3 hypomagnesemia an ECG is to be scheduled as soon as possible

- In the event of QT prolongation an ECG is to be performed prior to the next dose of Sym004
- As otherwise clinically indicated
- In the event of significant electrolyte abnormalities, the evaluation frequency should be increased to include additional evaluations between the scheduled assessments, as clinically indicated.

8.2.9 Laboratory Assessments and Pregnancy Test

All routine laboratory analyses will be performed at a laboratory facility local to the trial site. Results should be available to confirm eligibility and prior to each dosing of Sym004 and FOLFIRI.

Sponsor or designee must be provided with a list of trial site laboratory normal ranges for all required parameters prior to screening of the first patient at the site. Likewise, any change in laboratory normal ranges during the trial should be forwarded to the Sponsor or designee promptly during the trial.

Blood samples will be taken at all visits and analyzed for the following parameters as per [Table 16](#) and as clinically indicated:

Table 16 Schedule of Safety Blood and Urine Samples

Sample Analysis	Screening	Cycle 1				Cycles Thereafter		EOT	1M FUP
		D1	D8	D15	D22	D1	D15		
Day within Cycle									
Hematology Panel	X	X	X	X	X	X	X	X	X
Biochemistry Panel	X	X	X	X	X	X	X	X	X
Coagulation Panel	X	X	X	X	X	X	X	X	X
Urinalysis	X	X		X		X		X	X
Pregnancy Test	X							X	

Abbreviations (in alphabetical order): D, day; EOT, End of Treatment Visit; 1M FUP, One Month Follow-up Visit

8.2.9.1 Hematology Panel

To include complete blood count with differential, ANC, and platelet count.

- Screening
- Cycle 1
 - a. Day 1 and 15 (prior to dosing)
 - b. Day 8 and 22
- Each cycle thereafter

- a. Day 1 and 15 (prior to dosing)
 - EOT
 - 1M FUP
 - As clinically indicated

In the event of hematologic toxicity, the evaluation frequency should be increased to include additional evaluations between scheduled assessments, as clinically indicated.

8.2.9.2 Biochemistry Panel

To include, if applicable, sodium, potassium, chloride, bicarbonate or carbon dioxide, Blood Urea Nitrogen (BUN), creatinine, glucose, bilirubin [total and direct], AST, ALT, Alkaline Phosphatase (ALP), calcium, magnesium, phosphorus, albumin, total protein, uric acid, amylase, lipase, and Creatine Kinase (CK). Clinically significant electrolyte abnormalities should be corrected prior to dosing.

- Screening
- Cycle 1
 - a. Day 1 and 15 (prior to dosing)
 - b. Day 8 and 22
- Each cycle thereafter
 - a. Day 1 and 15 (prior to dosing)
- EOT
- 1M FUP
- As clinically indicated

In the event of significant biochemistry analyte abnormalities, the evaluation frequency should be increased to include additional evaluations between the scheduled assessments, as clinically indicated. In the event of CK abnormalities, isoenzyme analysis should be performed.

8.2.9.3 Coagulation Panel

To include PT, PTT and INR.

- Screening
- Cycle 1
 - a. Day 1 and 15 (prior to dosing)
 - b. Day 8 and 22

- Each cycle thereafter
 - a. Day 1 and 15 (prior to dosing)
- EOT
- 1M FUP
- As clinically indicated

8.2.9.4 Urinalysis

Multi-parameter chemical test strips are acceptable and should include assessment of: Specific gravity, pH, protein, glucose, ketones, leukocyte esterase, nitrite, bilirubin, and urobilinogen.

- Screening
- Cycle 1
 - a. Day 1 and 15 (prior to dosing)
- Day 1 of each cycle thereafter (prior dosing)
- EOT
- 1M FUP
- As clinically indicated

8.2.9.5 Pregnancy Test

Serum human Chorionic Gonadotropin (β -hCG) at screening, urine β -hCG thereafter, in women of childbearing potential.

- Screening
- EOT
- As clinically indicated

Women are considered of childbearing potential unless they have been hysterectomized, have undergone tubal ligation or have been postmenopausal for at least one year.

8.3 Disease Assessments

8.3.1 Tumor Marker Evaluation

To include Carcinoembryonic Antigen (CEA). Will be performed at a laboratory facility local to the trial site.

- Screening
- End of Cycle 2 and end of every second cycle thereafter, i.e. Cycle 4, 6, 8 etc.

NOTE: End of cycle assessments may be conducted at any time during the week prior to Day 1 of the next cycle

- At least 28 days following an OR (PR, CR)
- EOT (if > 3 weeks since previous evaluation)
- 1M FUP (if PD was not documented before or at EOT)

